**Summary Table of Study Protocol**

Title	Observational Study to Assess Maternal, Fetal, and Infant Outcomes Following Exposure to Erenumab-aooe During Pregnancy
Protocol version identifier	Original - Version 1.0
Date of last version of the protocol	Not Applicable
EU Post Authorization Study (PAS) Register No	Unavailable for first version
Active Substance	erenumab-aooe
Medicinal Product	Aimovig® (erenumab-aooe)
Product Reference	AMG 334
Procedure Number	NA
Joint Post-Authorization Safety Study (PASS)	Yes
Research Question and Objectives	
This study is being conducted to understand the safety of administering erenumab-aooe during pregnancy.
 
The primary objective is to estimate and compare the proportion of live-born infants with major congenital malformations among (1) women with migraine directly exposed to erenumab-aooe prior to or during pregnancy, (2) women with migraine exposed to other preventive migraine medications prior to or during pregnancy (comparator group A), and (3) women with migraine not exposed to erenumab-aooe or other preventive migraine medications prior to or during pregnancy (comparator group B). Comparative analyses will be undertaken if there is sufficient sample size and adequate overlap in the distribution of covariates to adjust for confounding.
 
Secondary objectives include estimation and comparison of the proportion of: 1) spontaneous abortions, and, separately, stillbirths, in pregnant women with migraine, and 2) 'small-for-gestational-age,' in live-born infants of women with migraine.

Country(ies) of Study	US
Author	PPD [REDACTED] PhD, Amgen, Inc PPD [REDACTED] PhD, Amgen Inc PPD [REDACTED] PhD, Amgen Inc PPD [REDACTED] PhD, HealthCore Inc PPD [REDACTED] PhD, HealthCore Inc

---

### Study Design Schema

[figure not shown]
Study design: Retrospective observational cohort study using data from MarketScan® Commercial Claims and Encounters databases and the HealthCore Integrated Research Database (HIRD)

Eligibility criteria for pregnant women with migraine: 1) Ages 16-44 years; 2) Evidence (diagnoses or acute medication use) of migraine prior to the last menstrual period (LMP); 3) Complete medical and pharmacy benefits; 4) Continuous health plan enrollment from 365 days prior to the LMP through the end of pregnancy

Eligibility criteria for live-born infants: 1) Infants from eligible pregnant women with migraine with record of live delivery and mother-infant linkage can be established; 2) Continuous enrollment for at least 90 days following birth

**Exposure period and definition:**

*Erenumab-aooe exposed:* claims for erenumab-aooe in the 112 days prior to the index date or during the pregnancy period  
*Comparator Cohort:* no claims for erenumab-aooe in the 112 days prior to the LMP or during the pregnancy period

**Multiple Pregnancies**  
 Women will be followed to capture multiple pregnancies during the study period. Subsequent pregnancy episodes will be identified by applying specific windows of time (min. number of weeks) between eligible pregnancy events outcomes. The length of the time window applied is contingent on type of first and subsequent pregnancy outcome.

## 2. List of Abbreviations

ACA	Affordable Care Act
CCE	MarketScan Commercial Claims and Encounters Databases
CFR	Code of Federal Register
CGRP	Calcitonin gene related peptide
CI	Confidence interval
CPT	Common Procedural Terminology
DRG	Diagnostic Related Groups
DSA	Data Sharing Agreement
EDC	Estimated date of conception
EOP	End of pregnancy
EU PAS	European Union Post-Authorization Studies Register
FDA	US Food and Drug Administration
HCPCS	Healthcare Common Procedure Coding System
HIRD	HealthCore Integrated Research Database
HIRE	HealthCore Integrated Research Environment
HIPAA	Health Insurance Portability and Accountability Act
ICD-10-CM	International Classification of Diseases, 10 th revision, Clinical Modification
ICMJE	International Committee of Medical Journal Editors
IPTW	Inverse probability of treatment weights
IQR	Interquartile range
LB	Live born
LMP	Last menstrual period
mAb	Monoclonal antibody
MACDP	Metropolitan Atlanta Congenital Defects Program
MRP	Medical record plan
NDC	National Drug Codes
NSAIDs	Nonsteroidal anti-inflammatory drugs
OR	Odds ratio
PASS	Post-authorization safety study
PHI	Protected health information
PPV	Positive predictive value
PS	Propensity score
SAP	Statistical analysis plan
SMD	Standardized mean difference
SD	Standard deviation
US	United States

### 4. Abstract

- Study Title: Observational study to assess maternal, fetal, and infant outcomes following exposure to erenumab-aooe during pregnancy
- Study Background and Rationale: Migraine is a neurological disorder characterized by recurrent headache attacks of moderate to severe pain. Erenumab is a human monoclonal antibody (mAb) that inhibits the receptor for calcitonin gene related peptide (CGRP) and is indicated for prevention of migraine headaches. Although clinical trials have demonstrated erenumab has a favorable risk benefit profile, there are no adequate and well-controlled studies on its use in pregnant women with migraine. This study is one of two studies being conducted to address post-market requirements [REDACTED] to assess the safety of erenumab-aooe on maternal, fetal, and infant outcomes resulting from the use of erenumab-aooe during pregnancy.

#### Research Question and Objectives

- Primary Objective  
The primary objective is to estimate and compare the proportion of live-born infants with major congenital malformations among (1) women with migraine directly exposed to erenumab-aooe prior to and during pregnancy, (2) women with migraine exposed to other preventive migraine medications prior to or during pregnancy (comparator group A), and (3) women with migraine not exposed to erenumab-aooe or other preventive migraine medications prior to or during pregnancy (comparator group B). Comparative analyses will be undertaken if there is sufficient sample size and adequate distribution of covariates to adjust for confounding.
- Secondary Objectives  
1) To estimate and compare the proportions of pregnancies ending in spontaneous abortions, and, separately, stillbirths among (1) women with migraine directly exposed to erenumab-aooe prior to and during pregnancy, (2) women with migraine exposed to other preventive migraine medications prior to or during pregnancy (comparator group A), and (3) women with migraine not exposed to erenumab-aooe or other preventive migraine medications prior to or during pregnancy (comparator group B). Comparative analyses will be undertaken if there is sufficient sample size and adequate distribution of covariates to adjust for confounding.

2) To estimate and compare the proportion of live-born infants who are small-for-gestational age among (1) women with migraine directly exposed to erenumab-aooe prior to and during pregnancy, (2) women with migraine exposed to other preventive migraine medications prior to or during pregnancy (comparator group A), and (3) women with migraine not exposed to erenumab-aooe or other preventive migraine medications prior to or during pregnancy (comparator group B). Comparative analyses will be undertaken if there is sufficient sample size and adequate distribution of covariates to adjust for confounding.

3) To describe demographic and clinical characteristics, risk factors for adverse pregnancy outcomes, fetal outcomes, and infant outcomes, and medication treatment patterns during pregnancy in both exposed and unexposed cohorts of women with migraine.

#### Hypothesis(es)/Estimation

If there is sufficient sample size and adequate overlap in the distribution of confounding variables, we will evaluate the null hypothesis of no effect of treatment on the four outcomes of interest. The proportion of spontaneous abortions, and, separately, stillbirths will be estimated and compared in pregnant women with migraine. Also, the proportion of major congenital malformations and, separately, 'small-for-gestational-age' will be estimated and compared in live-born infants of women with migraine.

#### Study Design/Type

Retrospective observational cohort study using administrative claims databases.

#### Study Population or Data Resource

Pregnant women with migraine in the US, ages 16-44 years of age, and who have private insurance. The study will use data from two automated commercial health insurance claims databases. The IBM Watson Health (formerly Truven Health) MarketScan Commercial Claims and Encounters (CCE) Databases includes claims from more than 200 US commercial health plans. The HealthCore Integrated Research DatabaseSM (HIRD) is a longitudinal claims database with medical coverage for 72.5 million unique individuals, and both medical and pharmacy coverage for 51 million unique individuals.

#### Summary of Patient Eligibility Criteria

Two cohorts of patients will be followed for outcomes:

- 1) Pregnant women with migraine, ages 16-44 years at the estimated date of conception
- 2) Live-born infants of pregnant women with migraine

See [Section 9.2.2](#) for a full list of eligibility criteria.

#### Follow-up

The study will start in November 2021 and end in November 2028. Because this study uses secondary data that has already been collected, data for analysis will be included starting from May 2018 when erenumab-aooe was approved in the US. Women will be followed for pregnancy outcomes (spontaneous abortion, and, separately, stillbirth) from their estimated LMP date through the end of their pregnancy date, and all live-born infants will be followed for outcomes from birth (eg, small-for-gestational age) through the end of their first year (eg, major congenital malformations). Women with migraine or their infants will be censored when their enrollment in the database ends.

#### Variables

##### *Outcome Variables*

###### *Primary:*

Major congenital malformations in live-born infants identified using ICD-10-CM diagnosis codes.

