## **8. Research Question and Objectives**

### **8.1 Primary**

The primary objective is to estimate and compare the proportion of live-born infants with major congenital malformations among (1) women with migraine directly exposed to erenumab-aooe prior to and during pregnancy, (2) women with migraine exposed to other preventive migraine medications prior to or during pregnancy (comparator group A), and (3) women with migraine not exposed to erenumab-aooe or other preventive migraine medications prior to or during pregnancy (comparator group B). Comparative analyses will be undertaken if there is sufficient sample size and adequate distribution of covariates to adjust for confounding.

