## 9.2.2 Subject/Patient/Healthcare Professional Eligibility

### 9.2.2.1 Inclusion Criteria

Two cohorts of patients will be followed for outcomes:

- 1) Pregnant women with migraine
- 2) Live-born infants of pregnant women with migraine

Inclusion criteria for the cohort of pregnant women with migraine are as follows:

- 1) Women who are pregnant and ages 16-44 years of age at estimated LMP date. Pregnancy will be defined using combinations of ICD-10-CM diagnosis codes and CPT procedure codes, which includes having evidence of at least one of the following pregnancy outcomes: spontaneous abortion, stillbirth, live birth, therapeutic abortion, or ectopic pregnancy.
- 2) Have evidence of migraine during the one year prior to the LMP date or during pregnancy, where migraine is defined using combinations of ICD-10 diagnosis codes for migraine and/or NDC or HCPCS codes for acute migraine medication use (eg, triptans or ergots). Patients will be included if they meet at least one of the following criteria:
  - a. 1 migraine diagnosis claim from a "non-emergency" inpatient visit
  - b. 1 migraine diagnosis claim from an outpatient visit associated with a neurologist (variable STDPROV 260 in MarketScan CCE)
  - c. 1 migraine diagnosis claim from an emergency room visit
  - d. 1 outpatient migraine diagnosis claim **PLUS** 1 acute migraine drug (triptan or ergot-derivative) prescription claim within 180 days of each other
  - e. 2 outpatient migraine diagnosis claims between 7 and 180 days apart
  - f. 2 acute migraine drug (triptan or ergot-derivative) prescription claims between 7 and 180 days

Have complete medical and pharmacy benefits coverage for the twelve months prior to the LMP date through a commercial health plan.

- 3) Have continuous enrollment in the health plan from 365 days prior to the estimated date of conception through the end of pregnancy

Inclusion criteria for the cohort of live-born infants of pregnant women with migraine are as follows:

- 1) Live-born infants (based on a live delivery record) from the cohort of pregnant women with migraine. In the HIRD, the subscriber ID is unique for all family members, and infants with birth dates or enrollment records within 30 days of delivery will be matched. Mother-child linkage in the Marketscan CCE database will be determined using the following criteria:
  - a. Mother's ID (minus last 2 digits) Infant's ID (minus last 2 digits)

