### **9.3.2 Outcome Assessment**

#### **9.3.2.1 Primary Outcome**

Major congenital malformations will be defined overall and by each malformation group using ICD-10-CM codes from the National Birth Defects Prevention Network (NBDPN) birth defects descriptions for the NBDPN core and recommended conditions including:

Central Nervous System (eg, anencephalus, spina bifida without anencephalus, encephalocele)

Eye (eg, anophthalmia/microphthalmia)

Ear (eg, anotia/microtia)

Cardiovascular (eg, common truncus, transposition of great arteries, tetralogy of fallot, ventricular septal defect, atrial septal defect, atrioventricular septal defect, pulmonary valve atresia and stenosis, tricuspid valve atresia and stenosis, Ebstein anomaly, aortic valve stenosis, hypoplastic left heart syndrome)

Orofacial (eg, cleft palate with and without cleft lip, choanal atresia)

Gastrointestinal (eg, esophageal atresia/tracheoesophageal fistula, rectal and large intestinal atresia/stenosis, small intestinal atresia/stenosis)

Genitourinary (eg, renal agenesis/hypoplasia, bladder exstrophy, hypospadias)

Musculoskeletal (eg, clubfoot, limb deficiencies, gastroschisis, omphalocele, diaphragmatic hernia)

See [Appendix D](#) for a full list of conditions and ICD-10 diagnosis codes

([https://www.nbdpn.org/docs/Appendix\\_3\\_1\\_BirthDefectsDescriptions2015\\_2016DEC14.pdf](https://www.nbdpn.org/docs/Appendix_3_1_BirthDefectsDescriptions2015_2016DEC14.pdf)). Outcomes that are not associated with drug exposure, such as chromosomal abnormalities, genetic syndromes, prematurity-related defects, and positional effects will be excluded from our definition of major congenital malformations. When linked medical records are available for validation studies conducted in the HealthCore Integrated Research Database, we will collect additional information on reasons (ie, chromosomal abnormality) for non-live births, including spontaneous abortions, where available.

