**Appendix D. ICD-10-CM and CPT Procedure Codes to Identify Outcomes: Major Congenital Malformations\***

ICD-10-CM diagnosis or CPT procedure codes	Description of codes
	Central Nervous System
Q00.0-Q00.1	Anencephalus
Q05.0-Q05.9, Q07.01, Q07.03 w/o Q00.0 - Q00.1	Spina bifida without anencephalus
Q01.0 – Q01.9	Encephalocele
	Eye
Q11.0 – Q11.2	Anophthalmia / microphthalmia
	Ear
Q16.0, Q17.2	Anotia/microtia
	Cardiovascular
Q23.0	Aortic valve stenosis
Q21.1	Atrial septal defect
Q21.2	Atrioventricular septal defect (Endocardial cushion defect)
Q25.1	Coarctation of the aorta
Q20.0	Common truncus (truncus arteriosus or TA)
Q20.1	Double outlet right ventricle (DORV)
Q22.5	Ebstein anomaly
Q23.4	Hypoplastic left heart syndrome
Q25.2, Q25.4	Interrupted aortic arch (IAA)
Q22.0, Q22.1	Pulmonary valve atresia and stenosis
Q20.4	Single Ventricle
Q21.3	Tetralogy of Fallot (TOF)
Q26.2	Total anomalous pulmonary venous connection (TAPVC)
Q20.3, Q20.5	Transposition of the great arteries (TGA)
Q22.4	Tricuspid valve atresia and stenosis
Q21.0	Ventricular septal defect
	Orofacial
Q30.0	Choanal atresia
Q37.0 – Q37.9	Cleft lip with cleft palate
Q36.0 – Q36.9	Cleft lip alone (without cleft palate)
Q35.1 – Q35.9	Cleft palate alone (without cleft lip)
	Gastrointestinal
Q39.0 – Q39.4	Esophageal atresia/tracheoesophageal fistula
Q42.0 – Q42.9	Rectal and large intestinal atresia/stenosis
Q41.0 – Q41.9	Small intestinal atresia/stenosis

\* Using the core and recommended birth defects from the NBDPN list of birth defects descriptions ([https://www.nbdpn.org/docs/Appendix\\_3\\_1\\_BirthDefectsDescriptions2015\\_2016DEC14.pdf](https://www.nbdpn.org/docs/Appendix_3_1_BirthDefectsDescriptions2015_2016DEC14.pdf))

ICD-10-CM diagnosis or CPT procedure codes	Description of codes
	Genitourinary
Q64.10, Q64.19	Bladder exstrophy
Q64.12	Cloacal exstrophy
Q64.2	Congenital Posterior Urethral Valves
Q54.0 – Q54.9 (excluding Q54.4)	Hypospadias
Q60.0 – Q60.6	Renal agenesis/hypoplasia
	Musculoskeletal
Q66.0, Q66.89	Clubfoot
Q79.0, Q79.1	Diaphragmatic hernia
Q79.3	Gastroschisis
Q71.0 – Q71.9, Q72.0 – Q72.9, Q73.0 – Q73.8	Limb deficiencies (reduction defects)
Q79.2	Omphalocele

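### Malformations are counted only in live-born infants, and terminations are identified but never analysed, so selective termination of affected pregnancies could attenuate the odds ratio unexamined

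*Protocol*

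**What the plan says.** The restriction to live births is consistent throughout the protocol. The Abstract gives the primary outcome as "Major congenital malformations in live-born infants identified using ICD-10-CM diagnosis codes". Section 8.1 states: "The primary objective is to estimate and compare the proportion of live-born infants with major congenital malformations among" the three cohorts. Section 9.2.2.1 builds the infant cohort from "Live-born infants (based on a live delivery record) from the cohort of pregnant women with migraine". Section 9.6.2.4.1 analyses infants born to each cohort.

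Terminations are nevertheless in the data. Section 9.2.2.1 defines pregnancy by "evidence of at least one of the following pregnancy outcomes: spontaneous abortion, stillbirth, live birth, therapeutic abortion, or ectopic pregnancy". Section 9.3.2.2 makes spontaneous abortion, stillbirth and small-for-gestational-age the secondary outcomes; therapeutic abortion is not among them. Section 9.3.4.1 seeks records to validate malformations, spontaneous abortion, stillbirth and LMP, and again does not name therapeutic abortion.

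Section 9.6.2.5.3 has two analyses specific to malformations. Both remain in live-born infants and vary only the follow-up or enrolment required after birth. Section 9.3.2.1 adds that, where HIRD records are linked, "we will collect additional information on reasons (ie, chromosomal abnormality) for non-live births, including spontaneous abortions, where available". The protocol names no analysis that uses this information. Section 9.8.1.2 discusses linkage, migraine identification and health-plan disenrolment, but not selection on live birth.

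**The concern.** The malformation list in Section 9.3.2.1 includes severe defects, for example "Central Nervous System (eg, anencephalus, spina bifida without anencephalus, encephalocele". If some affected pregnancies are detected before birth and terminated, those cases leave both numerator and denominator. If this happens equally in all cohorts, the relative measure hardly moves. If it happens more often in exposed women, the exposed cohort loses malformation cases selectively and the live-birth odds ratio falls below its true value. In a post-marketing safety study, bias towards no effect is the costly direction.

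A smaller gap concerns stillbirths. They are counted as stillbirths, but a malformation in a stillborn infant is never counted as a malformation. Followed exactly, the protocol would not let a reader of a null result tell absence of effect from selective termination.

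**Working it through.** **Inputs from the protocol (Section 9.5 and Table 2).** Malformation prevalence 3%; relative risk 2.00, so 6% in the exposed; 1:4 matching; 80% power; 425 exposed live births; mother-infant linkage about 77%; live-birth rate 62% (the Abstract gives 75-80%).

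**Assumed.** Two-sided alpha of 0.05, because Section 9.5 states no alpha. The loss shares below, because the protocol gives none. No differential loss of unaffected pregnancies.

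**Step 1: reproduce the plan's figure.** With p1 = 0.06, p0 = 0.03 and pooled p = (0.06 + 4 × 0.03)/5 = 0.036:

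n = [1.960 × √(1.25 × 0.036 × 0.964) + 0.842 × √(0.06 × 0.94 + 0.03 × 0.97/4)]² / 0.03² = (0.408 + 0.212)² / 0.0009 ≈ 428 at full precision.

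Table 2 states 425. Power at 425 is 79.8%. The figure reproduces.

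**Step 2: model for loss before live birth.** Let t be the share of affected pregnancies lost before live birth (tE exposed, tC comparator).

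- Observed risk among live births: q = p(1 − t)/(1 − pt).
- Simple approximation: observed RR ≈ 2.0 × (1 − tE)/(1 − tC).
- For the odds ratio, the planned measure, the odds q/(1 − q) equal p(1 − t)/(1 − p). The true odds ratio, (0.06/0.94)/(0.03/0.97) = 2.06, is therefore multiplied by exactly (1 − tE)/(1 − tC).

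**Step 3: results with a true RR of 2.0.** Power is for the unweighted comparison at 425 exposed and 1:4.

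| Comparator loss | Exposed loss | RR, simple | RR, fuller | Power |
|---|---|---|---|---|
| 10% | 10% | 2.00 | 2.01 | 76.4% |
| 20% | 20% | 2.00 | 2.01 | 72.4% |
| 2% | 5% | 1.94 | 1.94 | 75.4% |
| 5% | 10% | 1.89 | 1.90 | 71.4% |
| 10% | 20% | 1.78 | 1.79 | 60.5% |
| 20% | 30% | 1.75 | 1.77 | 54.3% |
| 20% | 40% | 1.50 | 1.53 | 32.8% |

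Example, 20% versus 30%: exposed 0.06 × 0.70/(1 − 0.018) = 0.0428; comparator 0.03 × 0.80/(1 − 0.006) = 0.0241; ratio 1.77.

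**Step 4: what full masking would need.** Setting the observed RR to 1.0, the exposed loss must be about 52%, 56% or 61% when comparator loss is 0%, 10% or 20%.

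**Step 5: linkage in a combined denominator.** Live births enter only if the infant is linked, about 77%. Terminations and stillbirths are seen in the mother's own claims and need no linkage. Adding them at full count would over-represent them by 1/0.77 = 1.30, so the remedy has to correct for this.

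**The case against.** The strongest reply is that the protocol is internally consistent here. The live-born endpoint is stated the same way everywhere, and further detail is deferred to the SAP and the Medical Record Plan, neither of which is shown. That stands: this is a design limitation, not an error or contradiction.

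Much is also already covered. Spontaneous abortion and stillbirth are estimated by cohort and compared if numbers allow (Sections 8.2 and 9.6.2.4.2). Prenatal testing is a listed covariate (Section 9.3.3), and covariates are summarised by cohort (Section 9.6.2.3.2). The sources of error named for the quantitative bias analysis are examples, not a closed list. A reader might infer that nothing in the plan would reveal the problem. That goes too far: excess fetal loss and heavier prenatal testing would both be visible. What remains uncovered is mainly termination, plus malformations within stillbirths.

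Two other stronger readings are tempting.

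- **That the design would hide a signal.** The documents do not show that erenumab users are tested more or terminate more, and the case is weakest against comparator group A, whose members also took preventive medication. The loss shares are applied to the whole malformation list, which also includes conditions such as clubfoot and hypospadias. Step 4 shows that complete masking needs more than half of affected exposed pregnancies to be lost.
- **That 38% of pregnancies (1 − 0.62) measures the gap.** The Abstract's 75-80% live-birth rate gives 20-25% instead. Both figures include spontaneous abortions and ectopic pregnancies, and neither is a share of malformations.

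**Conclusion.** The point holds as a limited, inexpensive improvement. On the protocol's text, malformations are never counted outside live births, terminations are identified and then left unanalysed, and selection on live birth is not among the biases considered.

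The possible effect runs from negligible to material. A true doubling would appear as about 1.94 under a small differential (2% versus 5%) and about 1.5 under a large one (20% versus 40%). Power at the planned 425 exposed live births would fall from 79.8% to 75.4% and 32.8% respectively. These values rest entirely on assumed loss shares and on the assumption that the loss is larger in exposed women. The documents support the statement that the odds ratio could be attenuated. They do not support the statement that it will be.

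**What to change.** Keep the live-born endpoint as primary and make three additions.

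1. **Section 9.6.2.5.3:** add one prespecified sensitivity analysis, run against each comparator group. The numerator adds therapeutic abortions and stillbirths that carry a fetal-malformation diagnosis in the mother's claims. The denominator adds all therapeutic abortions and all stillbirths. Put the outcomes on one footing in either of two ways: restrict live births to linked infants and weight the non-live outcomes for linkage (about 0.77 in MarketScan, with HIRD's own figure there), or ascertain all outcomes from maternal claims.
2. **Results:** report the therapeutic-abortion proportion by cohort beside the primary result, next to the prenatal-testing summary already planned.
3. **Section 9.8.1.2:** name selection on live birth and its likely direction if loss is greater in exposed women.

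The cost is two short code lists, since Appendices D to G contain none for therapeutic abortion or for fetal malformation in maternal claims, plus one further analysis on claims already extracted. Because therapeutic abortion is not named in the validation plan, HIRD records for these cases should not be assumed to be at hand. Maternal malformation codes are less specific than infant codes, so this should remain a sensitivity analysis. It does not recover losses before 20 weeks that are coded as spontaneous abortion.
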